
4.2 Study Endpoints

4.2.1 Primary Endpoint

Specific Aim 1

Primary Endpoints

- Peak mucosal eosinophil count at the time of enrollment from endoscopic biopsies obtained from the esophagus for EoE, stomach for EG, and colon for EC. The peak eosinophil count will be obtained from mucosal samples of each organ in 1 high power field.
- COM scores (see table 1) at one year intervals and clinically indicated visits and procedures.
- Correlation of peak mucosal eosinophil counts at the time of enrollment with the COM scores at one year intervals and at clinically indicated visits and procedures.

Table 1- COM metrics- (see below for descriptions)

PROs- Symptoms and QOL					
Metric	Rationale	Age	EoE	EG	EC
PEESSv2.0 Child/Teen Report	Assesses EoE symptoms	Peds	X	X	
PEESSv2.0 Parent Report	Assesses EoE symptoms	Parent	X	X	
PedsQL™ – Parents of Toddlers 2 – 4 years	Assesses EoE quality of life	Parent	X		
PedsQL™ – Young Children 5 – 7 years	Assesses EoE quality of life	Peds	X		
PedsQL™ – Parents of Young Children 5 – 7 years	Assesses EoE quality of life	Parent	X		
PedsQL™ – Children 8 – 12 years	Assesses EoE quality of life	Peds	X		
PedsQL™ – Parents of Children 8 – 12 years	Assesses EoE quality of life	Parent	X		
PedsQL™ –Adolescents 13 – 18 years	Assesses EoE quality of life	Peds	X		
PedsQL™ – Parents of Adolescents 13 – 18 years	Assesses EoE quality of life	Parent	X		
EEsAI	Assesses EoE symptoms	Adult	X		
EoE-QoL-A	Assesses EoE quality of life	Adult	X		
Likert Dyspepsia	Assesses gastric symptoms	Peds		X	
SODA	Assesses gastric symptoms	Adult		X	
PUCAI	Assesses colitic symptoms	Peds			X
SCCAI	Assesses colitic symptoms	Adult			X
PROMIS Peds Profile 25	Assesses general quality of life	Peds	X	X	X
PROMIS Adult Profile 29	Assesses general quality of life	Adult	X	X	X
Endoscopy					
Metric	Rationale	Age	EoE	EG	EC

EREFS	Assesses esophagitis	Both	X		
Lanza score	Assesses gastritis	Both		X	
UCCIS	Assesses colitis	Both			X
Histology					
Metric	Rationale	Age	EoE	EG	EC
EoE Biopsy Evaluation	Assesses esophageal eosinophilia and histologic features	Both	X		
EG Biopsy Evaluation	Assesses gastric eosinophilia and histologic features	Both		X	
EC Biopsy Evaluation	Assesses colonic eosinophilia and histologic features	Both			X
Exploratory					
Metric	Rationale	Age	EoE	EG	EC
EoE, EG, and EC transcriptome panel	Assesses gene expression for transcript phenotypes	Both	X	X	X

PRO-Symptoms and QOL

Pediatric EoE Symptom Score (PEESS)- PEESV2.0 is a pediatric PRO that contains patient and parent proxy instruments that can be easily understood. Scoring is based on two domains that evaluate frequency and severity of the symptoms reported by the patient (see Appendix). PEESV2.0 will be used to assess EoE symptoms. In addition, the PEESV2.0 will be used to assess pediatric EG as symptoms are similar to those present in EoE.

EoE Symptom Activity Index (EEsAI)- The EEsAI is an adult symptom module that has been content and face validated and represents an EoE-specific PRO. The EoE-QOL is an adult 37 item, 5 factor HRQL specific for adult EoE that has demonstrated excellent internal consistency.

Likert dyspepsia scale- Since no instruments are available to date for pediatric EG, we will use the Likert dyspepsia scale as an instrument to assess for related health.

Severity of Dyspepsia Assessment (SODA)- Since instruments are not available to date for adult EG, we will use the severity of dyspepsia assessment (SODA) scale as a validated instrument to assess dyspepsia related health.

Pediatric Ulcerative Colitis Activity Index (PUCAI)- The PUCAI is a validated pediatric objective measure used to standardize reporting of clinical ulcerative colitis activity. The index is composed of a 6-point scale that includes abdominal pain, rectal bleeding, stool consistency, number of stools, nocturnal stools and activity level. Scores range from 0-85 with a score of 45 being used for most studies indicating disease activity.

Simple Clinical Colitis Activity Index (SCCAI)- The SCCAI is a validated symptom based index (score 0–19) used to assess ulcerative colitis. It shows good correlation with other measures of ulcerative colitis disease activity. The SCCAI will be used to assess adult EC as symptoms are similar to those present in EC.

PedsQL™ 3.0- This instrument is a disease-specific measure of health-related quality of life for pediatric patients diagnosed with EoE.

EoE-QoL-A- The EoE-QoL-A is a self-reported questionnaire designed to assess disease-specific health related quality of life in adult EoE patients. Questions are designed to evaluate established domains of Health Related QOL, such as social functioning, emotional functioning, and disease impact on daily life experiences. It is a 37-item measure with five subscales: eating/dietary impact, social impact, emotional impact, disease anxiety and choking anxiety.

PROMIS- The PROMIS assessments selected for this study are multi-purpose, short-form health surveys with 29 and 25 questions respectively, that will be used for adult and pediatric EoE, EG, and EC. It yields a profile of general well-being.

Endoscopy

Endoscopic Reference System (EREFS)- The EREFS is a visual scoring tool developed to detect endoscopic features of EoE. EREFS was developed by CEGIR gastroenterologists and has been validated in adult subjects with active EoE by gastroenterologists with good inter-observer agreement. At time of endoscopy, an EREFS score will be assigned to the five central esophageal features of EoE (edema, rings, exudates, furrows, stricture). Training of endoscopists will be provided by [name] as to the use of the scoring system by means of a presently developed video library. [name] has developed a pictorial atlas with scoring criteria that will be provided to each investigator for reference. A score will be recorded for analysis with separate components for inflammatory and fibrostenotic features. If a procedure was completed prior to study entry, the endoscopic pictures and report will be used to generate an EREFS score.

Lanza Score-The Lanza score is an endoscopic grading system used to evaluate for gastritis. It has been used in therapeutic trials and is based on a 0-7 with 0=no lesions and 7= >3 mm ulcer scale. Since no system has been developed/used to date for EG, this score will be used to assess both pediatric and adult EG.

Ulcerative Colitis Colonoscopic Index of Severity (UCCIS)-This score was developed and validated for assessment of ulcerative colitis (UC). It is based on 6 components including vascular pattern, granularity, ulceration, and friability. Interobserver agreement is good to excellent and is correlated with clinical activity indices (R=0.52, p,0.001).

Histology

Pediatric and adult subjects with upcoming clinical endoscopy will be given the option to donate two – four (2-4) biopsies for this research. The research biopsies will be used for RNA and/or protein analysis. The immunological and histological analyses will generally be performed on the tissue normally taken for routine pathological evaluation.

Biopsy slide review- This study is multi-institutional and therefore biopsies will initially be reviewed by multiple different pathologists. We will ensure the integrity of the study and minimize variability in biopsy interpretation by having a Central Review Pathology Committee (CRPC), comprised of 3 pathologists who are experts in EoE, EG and EC biopsy interpretation. We will employ slide scanning and imaging software to achieve review by the CRPC.

Archived biopsy specimens upon which the subject's diagnosis was based prior to the start of this study will be scanned or sent to the Pathology Committee. If this is not possible because the original specimen was not obtained locally or is not available in the archive, a follow up biopsy with active disease will be scanned/sent for review by the Pathology Committee. If all subsequent diagnostic biopsies are inactive due to therapy then this will be noted in the subject file at DMCC and locally.

Biopsy specimens (original diagnostic and follow up collected during enrollment in study) will be scanned or sent to the Pathology Committee for review and agreement of the diagnosis will be confirmed with the local site. If the first endoscopy during the study is the diagnostic endoscopy and diagnostic criteria is not met, the subject will be withdrawn from the study.

For a subset of 30 subjects, the histology scoring tool will be tested for inter- and intra-observer reliability at baseline and end of treatment for acceptable variability.

Pathology Evaluation Forms- Esophageal, gastric and colonic pathology forms have been developed by [name], and approved by Drs. [name] and [name], with the goal of capturing features of eosinophilia relevant to the affected tissue and also other features indicative of mucosal health and

inflammation. All 3 pathology forms will be completed on-line by a pathologist. The final forms containing one set of scores for each biopsy will be submitted for data entry following resolution of differences among the pathologists. These numerical indices of eosinophil inflammation and associated pathology will be correlated to endoscopic and symptom metrics.

Specific Aim 2

Primary Endpoints

- Disease specific transcript profiles that distinguish EG from controls and EC from controls.
- Correlation of the pattern of gene expression in each disease with tissue eosinophil level for each disease.
- Correlation of dysregulated genes and other EoE-, EG-, and EC-related tissue features as described in Aim 1 (histology scoring tools).
- Resulting gene-of-interest (GOI) pool validated by qPCR and/or protein detection. We are planning on performing a genome wide expression (transcriptome) analysis of biopsy derived RNA. After we identify genes of interest, we will validate their expression changes by qPCR and/or protein detection (e.g. ELISA, Western Blot analysis, etc).
- Set of diagnostic genes embedded into a PCR-based high throughput fluid card. Similar to the EoE Diagnostic Panel, we will consider embedding the informative genes into a custom array, based on the ABI fluid card PCR system.

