3.1 Primary Objective

Specific Aim 1- Determine the correlation of EoE, EG, and EC clinical outcome measures (COMs) with mucosal eosinophilia.

Primary Objective-To perform a prospective, multicenter, pediatric and adult longitudinal study to determine the correlation of COMs (PROs, QoL and endoscopy) with the established biomarker of peak mucosal eosinophil count (Phase 1).

Hypotheses: The overriding hypothesis of this aim is that clinical outcome measures (COMs) will correlate with the standard biomarker of mucosal eosinophilia in subjects with EoE, EG, and EC. In addition, we will test a series of other hypotheses to help determine phenotypes associated with EoE, EG and EC. The overall aim of these studies will be to measure clinical features of pediatric and adult EoE, EG, and EC in a cross sectional and longitudinal study and correlate these findings with the standard biomarker, mucosal eosinophilia. Clinical endpoints include pediatric and adult specific COMs such as patient-reported outcomes (PROs), quality-of-life (QoL) scales, endoscopic scores, and the histological endpoint peak will be mucosal eosinophil count in the respective organ (EoE-esophagus, EG-stomach, EC-colon).

Specific Aim 2- Determine the correlation of the molecular profile for EoE, EG, and EC with clinical outcome measures (COMs) and mucosal eosinophilia.

August 8, 2016

Primary Objective-To perform a prospective, multicenter, pediatric and adult exploratory study to compare the transcriptomes (EoE-transcriptome, EG-transcriptome and EC-transcriptome) with their respective peak mucosal eosinophil counts and respective COMs generated in Aim 1.

Hypothesis: We hypothesize that there is a disease specific mRNA expression profile in EoE, EG and EC that will associate with tissue eosinophil counts and COMs.

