8.1 Screening

Subjects enrolled will have a confirmed diagnosis of EoE, EG or EC regardless of their treatment status as we are interested in the relationship between mucosal inflammation, whether currently present or not, with the COMs. Patients who are recruited will either have an established diagnosis of EoE, EG or EC and are undergoing SOC endoscopic analysis at the point of entry or will be patients who are undergoing endoscopy to establish a new diagnosis of EoE, EG or EC. *If EoE, EG, or EC diagnosis is new, enrollment and COM completion will occur within 4 weeks of the diagnostic endoscopy and prior to any treatments for their disease so that the impact of treatments will not impact any of the COMs.*

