12.5 Final analysis plan

The research study will be explained in lay terms to each potential research participant. The potential participant will sign an informed consent form before undergoing any study procedures. Once the informed consent has been signed, the participant is considered enrolled in the study and will be assigned a unique participant number. Each enrolled subject becomes part of the longitudinal study.

AIM 1: We will perform intergroup and intragroup baseline analysis at study entry, longitudinal analysis, and supportive and exploratory analysis with the expertise of our statisticians Drs. [name] and [name]. To describe the clinical profile for each disease entity, separate analysis will be performed at baseline for participants in the newly diagnosed cohort and the previously

diagnosed (ongoing cohort). Summary statistics, grouped by adults or children, will be calculated for the demographic and the outcome variables. Differences in these phenotypic variables between EoE, EG, and EC will be tested using ANOVA or chi square tests. To evaluate the correlation of peak eosinophils with COMs (e.g. PROs, EREFS, QoL metrics), multivariate regression analysis will be conducted separately for each COM, with the COM serving as the dependent variable and peak eosinophil counts as the independent variable. Covariates in the model will include, but are not limited to, sex, age group, atopic disease, race, disease duration, and medication usage. To assess the difference in the extent of this correlation between cohorts or age groups, an interaction term of peak eosinophil counts by the selected categorical variable will be introduced to and tested under the above model. Similarly, PROs will be correlated with the other endoscopy (EREFs, Lanza score, UCCIS) and histology (biopsy evaluation forms) measures using the same approach. The normality assumptions will be evaluated, and transformations will be used (e.g. square root, log, rank) as appropriate. The correlation analyses discussed above will be conducted separately for EoE, EG, and EC.

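### Section 4.2.1 pairs the enrolment eosinophil count with follow-up COM scores and leaves out the enrolment COM scores, which fits neither the Phase 1 objective nor either analysis in section 12.5

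*Protocol*

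**What the plan says.** Section 4.2.1 lists three primary endpoints for Aim 1: the peak count at enrolment, COM scores during follow-up, and the correlation of the two. The third begins "Correlation of peak mucosal eosinophil counts at the time of enrollment with the COM scores at one year intervals"; its COM clause in full is "with the COM scores at one year intervals and at clinically indicated visits and procedures". None of the three bullets names a COM score taken at enrolment.

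Other sections set the timing differently:

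- Section 3.1 states the primary objective as to "determine the correlation of COMs (PROs, QoL and endoscopy) with the established biomarker of peak mucosal eosinophil count (Phase 1"). It also describes the work as done "in a cross sectional and longitudinal study and correlate these findings with the standard biomarker, mucosal eosinophilia".
- Section 8.1 says of new diagnoses that "enrollment and COM completion will occur within 4 weeks of the diagnostic endoscopy and prior to any treatments for their disease". The reason given is to keep treatment from influencing the COMs.
- Section 8.4 places the yearly, treatment-change and later endoscopy assessments in Phase 2, which section 3.2 makes the secondary objective. Without an endoscopy, only symptom and quality-of-life questionnaires are completed.
- Section 12.5 opens Aim 1 with "We will perform intergroup and intragroup baseline analysis at study entry" and then regresses each COM on the peak count. Its longitudinal part regresses one-year change in COM on one-year change in count, and calls that one-year change the primary endpoint as well.
- Appendix B schedules every COM, including the endoscopic scores and biopsy evaluations, at recruitment.

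**The concern.** A primary endpoint should state which count goes with which score. Section 4.2.1 holds the count at enrolment while the COM moves forward in time. For a newly diagnosed patient that sets a pre-treatment count against scores taken after treatment may have begun. Such a correlation reflects the eosinophil-COM relation, the treatment given in between and the patient's response to it. A weak result could then be read as evidence that eosinophils do not track clinical outcome, when the pairing itself may have produced it. Section 2.1.2 names that link as a major focus of the study.

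There is also a question of choice. With one definition in section 4.2.1 and two others in section 12.5, the result to be called primary could be settled after the data are seen.

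**Working it through.** **1. The passages side by side.**

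| Protocol section | Eosinophil count | COM score | Status given |
|---|---|---|---|
| 4.2.1, third bullet | enrolment | yearly, and at clinically prompted visits and procedures | primary endpoint |
| 3.1 | Phase 1, no date | Phase 1, no date | primary objective |
| 8.1, new diagnoses | diagnostic endoscopy | within 4 weeks, before treatment | timing at entry |
| 12.5, first regression | introduced as analysis at entry | introduced as analysis at entry | correlation analysis |
| 12.5, longitudinal | change over one year | change over one year | also called primary endpoint |
| 8.4, annual visit | none without an endoscopy | questionnaires only | Phase 2, secondary |
| Appendix B, recruitment | biopsy evaluation | all COMs | collected |

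**2. What follows.**

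- The pairing in the first row appears in neither analysis of section 12.5. In the first regression, count and COM belong to the same occasion. In the longitudinal one, both are changes over the same interval.
- The primary objective covers endoscopic measures. At an annual visit without an endoscopy these do not exist, so part of the endpoint in 4.2.1 cannot be computed at yearly intervals.
- A later clinically prompted endoscopy yields its own count (section 8.4), yet 4.2.1 still uses the enrolment count.
- The enrolment COM scores needed for a same-time pairing are already collected.

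**3. The plan's own sample-size figures.** Section 12.4 gives alpha 0.01 and 80% power without stating sidedness; two-sided is assumed here. For an unadjusted correlation, Fisher's z gives

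minimum r = tanh[(2.576 + 0.842) / √(n − 3)].

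- EC, n = 150: tanh(3.418 / 12.124) = 0.275, stated 0.27
- EG, n = 300: tanh(3.418 / 17.234) = 0.196, stated 0.20
- EoE, n = 600: tanh(3.418 / 24.434) = 0.139, stated 0.14

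The unadjusted column of Table 3 reproduces within rounding. (The adjusted column does not fully do so: at its stated R² values with 6 covariates, power is 77.2% for EC, 67.5% for EG and 82.0% for EoE. That is a separate matter and is not used here.) Table 3 has no term for a time lag, so a same-time pairing leaves it and the sample size unchanged.

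**4. Illustration only.** Assume the enrolment count bears on a later COM only through the later count. The lagged correlation is then k × r, where k is the within-person correlation of counts. The protocol gives no k, so a range is shown. Power = Φ[atanh(k·r)·√(n − 3) − 2.576]. For EC with k = 0.5: atanh(0.135) × 12.124 = 1.647, and Φ(1.647 − 2.576) = 18%.

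| k | EC, r = 0.27 | EG, r = 0.20 | EoE, r = 0.14 |
|---|---|---|---|
| 1.0 | 78% | 82% | 81% |
| 0.8 | 53% | 58% | 57% |
| 0.5 | 18% | 20% | 19% |
| 0.3 | 6% | 6% | 6% |

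The table also treats every COM as lagged, which the text of 4.2.1 does not require. It shows how sensitive a lagged endpoint could be. It is not an estimate for this study, and the contradiction in step 1 does not depend on it.

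**The case against.** The best defence is that the trial will not analyse what section 4.2.1 literally says. Section 12.5 plans no regression of later COMs on the enrolment count, and section 12.3 describes the protocol as exploratory. That stands in part: the harm arises only if 4.2.1 is followed as written. But 4.2.1 is where the primary endpoint is defined, and its conflict with section 12.5 is the point at issue.

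Three stronger readings are tempting, and the protocol does not support them.

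- *Every COM in the endpoint is a year or more later.* The sentence also covers clinically prompted visits and procedures. These can fall within the first year and might even be read to include the entry endoscopy. The wording is ambiguous, not exclusively lagged.
- *Aim 1 seeks only a same-time correlation at entry.* Section 3.1 names both a cross-sectional and a longitudinal study, and section 12.5 calls a one-year change primary. The same-time target is partly inferred, chiefly from sections 8.1 and 12.5.
- *Established patients may enter on an endoscopy of any age.* Section 8.1 describes them as having their endoscopy on entry. Sections 4.1, 4.2.1 and 8.2 allow for a procedure already completed, but that may refer to new diagnoses, who are also enrolled after endoscopy. The 4-week limit is written only for new diagnoses; beyond that, the position of established patients is unclear rather than open-ended.

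**Conclusion.** The point holds as a contradiction about the primary endpoint in the protocol's current text. Section 4.2.1 states a pairing that neither analysis in section 12.5 carries out, omits the enrolment COM scores, and relies on endoscopic scores that annual visits do not supply. Section 12.5 attaches the primary label to something else again. This is a rule stated wrongly, not detail that can wait for a statistical analysis plan.

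Taken literally, the endpoint confounds the eosinophil-COM relation with intervening treatment. By how much is unknown. A reader might infer from the illustration that the study is underpowered, but k, mediation solely through the later count and the lagging of every COM are all assumptions from outside the protocol. No data are lost, and the planned 600, 300 and 150 patients are unaffected.

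**What to change.** Reword the second and third bullets of section 4.2.1 along these lines:

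- *COM scores completed at enrolment.*
- *Correlation of the enrolment peak eosinophil count with the COM scores completed at enrolment. COM scores at any later endoscopy are paired with the peak count from that same endoscopy. The correlation of the enrolment count with later COM scores is exploratory.*

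In section 12.5, state that the first regression uses the enrolment pair, and label the one-year change-on-change analysis as the endpoint of the longitudinal (Phase 2, secondary) objective.

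For established patients whose endoscopy preceded entry, record the interval from endoscopy to COM completion and add a sensitivity analysis restricted to short intervals. A new eligibility window is not needed.

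The cost is a change of wording in two sections, one recorded interval and one sensitivity analysis. No visit, sample or patient is added, because Appendix B already schedules the COMs at recruitment.

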4.1 Description of the Study Design

Specific Aim 1: Primary Objective (Phase 1)-We will conduct a prospective, observational study that will measure COMs and peak mucosal eosinophilia in pediatric and adult subjects with EoE, EG and EC. Subjects will be recruited by investigators located at multiple academic and research medical centers. Subjects will be enrolled who have a confirmed diagnosis of EoE, EG or EC regardless of

their treatment status, as we are interested in the relationship between mucosal inflammation, whether present or not, with the COMs.

Three groups of patients will be recruited; 1.) patients with an established diagnosis of EoE, EG or EC 2.) patients who have a new diagnosis of EoE, EG or EC and 3) healthy controls that are having endoscopy and/or colonoscopy (this group is for the mechanistic microbiome study). The second group will be enrolled within 4 weeks of the diagnostic endoscopy and prior to any treatments for their disease. Recruited patients will then 1.) sign informed consent, 2.) undergo standard of care (SOC) evaluation to capture defined clinical data, 3.) complete questionnaires, and 4.) analysis of their formalin-fixed, paraffin-embedded (FFPE) esophageal, gastric, or colonic biopsy (obtained as part of SOC) to measure peak eosinophil count and associated features. At the time of SOC endoscopy, subjects who have consented to have research biopsies collected will provide two to four additional biopsies for RNA and microbiome analysis (this will be repeated at each SOC endoscopy during the course of the study). At the time of the SOC endoscopy post enrollment (microbiome sub-study participants are not in study after the first SOC procedure is completed), subjects who have consented to donate blood/saliva/stool for this study will provide 10-15 mls of blood and/or 2 ml of saliva for DNA analysis and stool for storage and for microbiome analysis (see sub studies). At the time of endoscopy, one photograph image will be captured from the site of the research biopsies.

Correlation of COMs with peak eosinophil counts will lead to development of an understanding of optimal COM to measure disease activity. If an endoscopy is to be scheduled, the endoscopic score will be assigned at the time of the procedure. If the endoscopy has been already completed, the score will be performed on the recorded video/pictures as described below. Instructions and administering the COMs will be coordinated at each enrollment site.

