7.1 Use of Stored Samples/Data

If an endoscopy is to be scheduled, the endoscopic score will be assigned at the time of the procedure. If the endoscopy has been already completed, the score will be performed on the recorded video/pictures.

Archived tissue (biopsy slides) will be evaluated by immunohistochemical staining as described previously.

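### Endoscopic scores are made live for some patients and afterwards for others, with no masking to the biopsy result and no record of which, so the endoscopy–eosinophil correlation is open to bias of unknown size

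*Protocol*

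**What the plan says.** Section 4.1 gives two rules for endoscopic scores in general: "If an endoscopy is to be scheduled, the endoscopic score will be assigned at the time of the procedure", and "If the endoscopy has been already completed, the score will be performed on the recorded video/pictures as described below". Section 7.1 repeats the second: "If the endoscopy has been already completed, the score will be performed on the recorded video/pictures". For EREFS, section 4.2.1 names different material: "If a procedure was completed prior to study entry, the endoscopic pictures and report will be used to generate an EREFS score". It provides training and an atlas for EREFS, but does not say who makes a retrospective score or what that person may have seen.

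On the timing of entry for newly diagnosed patients, section 4.1 says: "The second group will be enrolled within 4 weeks of the diagnostic endoscopy and prior to any treatments for their disease". Section 8.1 describes established patients as those who "are undergoing SOC endoscopic analysis at the point of entry or will be patients who are undergoing endoscopy to establish a new diagnosis", the second half of that phrase being the new-diagnosis group. Section 4.2.1 also provides for a diagnostic endoscopy inside the study, with withdrawal as the consequence: "If the first endoscopy during the study is the diagnostic endoscopy and diagnostic criteria is not met".

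In section 12.5 each clinical outcome measure, EREFS included, is the dependent variable and peak eosinophil count the independent variable. The named covariates do not include scoring mode, although the list is open. The section continues: "To assess the difference in the extent of this correlation between cohorts or age groups, an interaction term of peak eosinophil counts".

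**The concern.** The endoscopic score and the eosinophil count are the two sides of an Aim 1 regression. A live score is made before that procedure's histology exists. A retrospective score can be made by someone who already knows the count. Such a scorer may grade subtle features such as edema, exudates or furrows in line with it, which ties the dependent variable to the independent one.

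Two results are at stake. The first is the endoscopy–eosinophil correlation itself. Section 4.1 says the correlations will guide the choice of the best measure of disease activity, and patient- or parent-completed outcomes are not exposed to this scorer effect. The second is the comparison of newly and previously diagnosed patients: if the share scored retrospectively differs between them, a difference in correlation may come from the scoring.

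**Working it through.** **1. Is the count normally known when a retrospective score is made?** The protocol does not say so, but its steps imply it for patients enrolled after a diagnostic biopsy.
- An eosinophil threshold is an entry criterion (Table 2a).
- The local pathologist counts first and central review verifies later (section 8.3).
- The site attests to eligibility at registration (section 15.2.1).

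The local count is therefore normally at the site. The centrally reviewed value may differ from it.

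**2. Does scoring mode follow cohort?** Only in part.
- Towards retrospective scoring of new patients: the 4-week window after the diagnostic endoscopy (sections 4.1 and 8.1), and Appendix B, which lists endoscopic scores at recruitment separately from the standard-of-care endoscopy.
- Towards live scoring of new patients: sections 8.1 and 8.2, where they are undergoing the diagnostic endoscopy, and the in-study diagnostic endoscopy in section 4.2.1.
- Established patients are described as having endoscopy at entry, which implies live scoring.

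The protocol gives no share for either cohort.

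**3. The plan's own benchmark.** Section 12.4 claims at least 80% power for a correlation of 0.14 (R² increase 0.02) in 600 EoE patients, with alpha 0.01 and 6 covariates.
- F test, taking the covariates to explain no variance: noncentrality = 600 × 0.02 / 0.98 = 12.2 on 1 and 592 degrees of freedom. Power is 82%.
- Fisher z, two-sided: atanh(0.14) × √597 − 2.576 = 0.87. Power is 81%.

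The figure reproduces. It neither supports nor refutes the point, but it shows that correlations of this size are treated as meaningful.

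**4. Possible effect on the pooled correlation (assumed inputs).** Let the live score have standardised slope ρ on the count and the retrospective score slope ρ + b, with a share f scored retrospectively. Then

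r = (ρ + f·b) / √[1 − ρ² + f(ρ + b)² + (1 − f)ρ²].

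With ρ = 0.14:

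| b | f = 0.25 | f = 0.5 | f = 1 |
|---|---|---|---|
| 0 | 0.140 | 0.140 | 0.140 |
| 0.1 | 0.164 | 0.188 | 0.236 |
| 0.2 | 0.188 | 0.234 | 0.325 |

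For example, b = 0.1 and f = 0.5 give 0.19 / √1.019 = 0.188. If the true correlation is 0, an induced r of 0.05 or 0.10 in 600 patients would be significant at 0.01 in about 9% or 45% of studies.

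**5. The opposite direction.** If image scoring only adds noise, the correlation in that subset is ρ√reliability: 0.14 × √0.7 = 0.117 and 0.14 × √0.9 = 0.133.

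**6. Possible effect on the cohort interaction (assumed inputs).** Take 300 patients per cohort, a true slope of 0.20 in both, and every new patient but no established patient scored retrospectively. The standard error of the slope difference is √(2 × 0.96 / 300) = 0.080.

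| b | z | significant at 0.05 | significant at 0.01 |
|---|---|---|---|
| 0.1 | 1.25 | 24% | 9% |
| 0.2 | 2.50 | 71% | 47% |
| 0.3 | 3.75 | 96% | 88% |

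This is the extreme alignment. In general the slope difference is about b × (retrospective share in new − share in established). If half of the new patients are scored live, b = 0.2 yields a difference of 0.10 and a rate of about 24%, not 71%.

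**The case against.** A reader might infer that the correlation is biased, upwards, and mostly in the newly diagnosed cohort. The documents do not support that. They do not say who scores retrospectively or what that person knows, and operating detail is left to a manual that is not shown. The direction is not fixed either, since image noise weakens a correlation. The retrospective rule applies to any procedure before entry, whatever the cohort, and part of the new cohort can be scored live. All of this stands.

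It can also be said that a scorer who knows only that the threshold was passed would shift the level of the score, not the slope, and that a cohort main effect would absorb such a shift. That is fair, and it is one reason why the rates in step 6 illustrate the mechanism and do not estimate it for this study.

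A reader might further take sections 4.1 and 7.1 to permit images only, in conflict with the EREFS rule. Neither says only, and section 4.1 points forward to the later description. The wordings differ and should be reconciled, but they are not in flat contradiction. Dropping the report would also have a price, because it may describe what the pictures miss.

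Finally, covariates and sensitivity analyses can be left to an analysis plan, and section 12.3 calls the work more exploratory than validating. That is true of the model terms. It does not cover masking or the recording of scoring mode: these are matters of conduct, and no later analysis can supply them reliably if they were not done at the time.

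**Conclusion.** The point holds as an exposure to bias, not as a demonstrated bias. Two scoring modes feed the same Aim 1 variable. For patients enrolled after a diagnostic biopsy the local count is normally available, and the protocol neither masks the retrospective scorer nor requires the mode to be captured. The cohort interaction for endoscopic scores may partly reflect scoring mode, because retrospective scoring is likely, though not shown, to be more common in new patients.

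The size is unknown: the protocol gives neither the share scored retrospectively nor the influence of a known count. Under the assumed values above, a true correlation of 0.14 could appear as 0.16 to 0.33 with a scorer effect, or as 0.12 to 0.13 within the retrospective subset with image noise alone. The EREFS passage covers only that score; sections 4.1 and 7.1 carry the point to Lanza and UCCIS.

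**What to change.** - Record scoring mode, live or retrospective, in the CRF for every EREFS, Lanza and UCCIS score.
- In each model with an endoscopic score, include mode and a mode-by-eosinophil-count term. Mode as a main effect alone corrects the level and leaves a slope bias untouched.
- Add a sensitivity analysis on live-scored procedures only. Interpret the cohort interaction for endoscopic scores cautiously unless it is consistent there; if too few new patients were scored live to judge, say so.
- State in sections 4.1, 4.2.1 and 7.1 that a retrospective score is made by an already trained site endoscopist who has not seen the pathology result, where one is available. Flag the score as unmasked otherwise.
- Reconcile the material to be scored between section 4.2.1 (pictures plus report) and sections 4.1 and 7.1 (video or pictures), and state it for Lanza and UCCIS as well.

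The cost is a few sentences, one CRF field, a little more analysis, and lower precision in the live-only analysis. It needs no new visits or procedures. Requiring a live score for all newly diagnosed patients is not proposed, because it could not reach those whom the protocol allows to enrol after the endoscopy.
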